older than 40 years [20]. In experienced centers, similar results can be obtained after oocyte cryopreservation [21,22]. Of note, so far, limited data are available on the success of embryo/oocyte cryopreservation after controlled ovarian stimulation in cancer patients. To date, the largest series of pregnancy and fertility outcomes reported in the specific subgroup of breast cancer patients was described by Oktay and colleagues in 2015 [23]. In this single-center prospective cohort study, 131 women diagnosed with stage I-III breast cancer and aged  $\leq 45$  years, underwent controlled ovarian stimulation (with a protocol that included letrozole) followed by embryo cryopreservation before the initiation of anticancer therapy. Oocytes were fertilized by intracytoplasmic sperm injection, and all embryos were cryopreserved via a vitrification method. After a median time of 5.25 years following oocyte retrieval, 33 breast cancer survivors returned to undergo frozen embryo transfer to self or used a gestational carrier. Embryo post-thaw survival rate was 84.4%; 40 frozen embryo transfers were performed with the embryos from these 33 breast cancer survivors (mean number of embryos transferred = 1.97). The authors observed an overall clinical pregnancy rate (defined as the presence of at least one gestational sac at the time of the first ultrasound examination by the eight week of gestation) of 65.0% (26/40), a live birth rate per embryo transfer of 45.0% (18/40), and an implantation rate (defined as the total number of pregnancy sacs per total number of embryos transferred) of 40.7% (33/81). These data did not differ from those reported by the American Society of Assisted Reproductive Technology in a comparable non-oncologic age group (age 35 to 37 years) and time period (2009). A total of 25 children were born from 18 pregnancies without fetal anomalies or malformations, developmental problems or any medical complications during pregnancies or the postpartum period. Out of the 33 breast cancer survivors attempting pregnancy, 20 women had at least one pregnancy: three patients had spontaneous abortions, bringing the fertility preservation rate (defined as the percentage of women obtaining at least one live birth among all who attempted a frozen embryo transfer) to 51.5% per attempting woman. The self transfer and gestational carrier groups had similar pregnancy outcomes, clinical pregnancy, and live birth rates [23]. Although these

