#### Inclusion criteria:

- Diagnosis of invasive non-metastatic breast cancer (i.e. stage I to III);
- Breast cancer diagnosis  $\geq 18$  and  $\leq 40$  years;
- No prior history of gonadotoxic treatments;
- Fertility preservation counseling for fertility preservation;
- Written inform consent;
- FSH  $< 20$  UI/L and/or antra-follicular count  $\geq 6$  (follicles of 2-9 mm) and/or AMH  $\geq 6$  pmol (only applicable for patients who undergo controlled ovarian stimulation for embryo/oocyte cryopreservation).

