## 5. STATISTICS

Three cohorts of patients will be prospectively included in the study (Figure 1 in the Appendix):

**1) Letrozole-stimulated cohort:** this includes all newly diagnosed breast cancer who are candidates to receive (neo)adjuvant chemotherapy and undergo oocyte/embryo cryopreservation at the Belgian participating centres.

**2) Standard-stimulated cohort:** this includes all newly diagnosed breast cancer who are candidates to receive (neo)adjuvant chemotherapy and undergo oocyte/embryo cryopreservation at the French participating centres.

**3) Non-stimulated cohort:** this includes all newly diagnosed breast cancer who are candidates to receive (neo)adjuvant chemotherapy who have access to the Fertility Clinics in all the participating centres but are not willing to undergo oocyte/embryo cryopreservation. Patient who underwent another fertility preservation procedure (ovarian tissue cryopreservation, GnRH analogues,...) are eligible in this cohort.

All the efficacy analyses will be performed to compare the letrozole-stimulated cohort and the standard-stimulated cohort. All the safety analyses will be conducted to compare separately the letrozole-stimulated cohort with the non-stimulated cohort and the standard-stimulated cohort with the non-stimulated cohort.

To evaluate the efficacy of performing a controlled ovarian stimulation with or without letrozole in young women with newly diagnosed breast cancer who are candidates to receive (neo)adjuvant chemotherapy, the following endpoints will be assessed:

- Number of mature oocytes collected (primary endpoint).
- Number of oocytes collected;
- Maturation rate: defined as ratio between the number of mature oocyte collected and total number of oocyte collected;
- Number of oocyte/embryo cryopreserved;
- Number of patients with poor response: defined as retrieval of  $\leq 4$  oocytes;
- Number of patients with stimulation failure: defined as no follicular growth after 1 week of adequate controlled ovarian stimulation administration.

The efficacy of performing controlled ovarian stimulation with or without letrozole will be evaluated also in various subgroups of young women with newly diagnosed breast cancer who are candidates to receive (neo)adjuvant chemotherapy according to the following characteristics:

- Type of stimulation: follicular vs. random;
- Hormone receptor status: positive vs. negative;
- Presence of *BRCA* mutation: *BRCA*-mutated vs. *BRCA*-not mutated.

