The impact of anticancer therapies on patients' ovarian function will be evaluated in various subgroups of young breast cancer patients according to:

- Age: <30 vs. 30-35 vs. > 35;
- Type of chemotherapy received: anthracycline- and taxane-based vs. taxane-based vs. others;
- Number of months of chemotherapy received: <4 months vs. > 4 months;
- Exposure to platinum agents: use vs. no use.
- Exposure to endocrine therapy: use vs. no use.
- Exposure to anti-HER2 therapy: use vs. no use.
- Presence of *BRCA* mutation: *BRCA*-mutated vs. *BRCA*-not mutated.

The sample size has been estimated based on the study primary endpoint (i.e. number of mature oocytes collected). With 113 patients in the standard-stimulated cohort and 113 in the letrozole-stimulated cohort, assuming a mean number of mature oocytes collected of 6.1 in the standard-stimulated cohort, the study will have a power of 0.80 to reject the null hypothesis of equal means when the population mean difference is 1.5 mature oocytes collected (estimating a mean number of mature oocytes collected of 7.6 in the letrozole-stimulated cohort) with a standard deviation for both groups of 4.0 and with a significance level (alpha) of 0.05 using a two-sided two-sample equal-variance t-test. Considering that approximately one out of three (1:3) eligible patients counseled to

undergo controlled ovarian stimulation for oocyte cryopreservation before starting anticancer treatments will accept the procedure, it is estimated to enroll 339 patients in the non-stimulated cohort.

Patients demographic, clinical and pathologic baseline characteristics will be compared in the three cohorts using chi-square test or Fisher Exact test for categorical variables and Wilcoxon rank-sum test or t-test for continuous variables, as appropriate.

Dicothomous outcomes will be compared using univariate and multivariate logistic regression models. Time-to-event outcomes will be estimated and plotted using Kaplan-Meier methods. Survival rates will be compared using log-rank test and Cox proportional hazards models for univariate and multivariate analysis, respectively.

All tests will be two-sided and p-values of  $< 0.05$  will be considered statistically significant.

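### Section 5 prescribes logistic regression for every dichotomous outcome with no provision for few or zero events, so sparse secondary outcomes may have no usable estimate

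*Combined protocol and SAP*

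**What the plan says.** One sentence in Section 5, repeated in the Statistics row of the synopsis, covers all binary outcomes: "Dicothomous outcomes will be compared using univariate and multivariate logistic regression models". It names no estimation method, no test (Wald, likelihood ratio or score), no covariates and no rule for zero cells. The preceding paragraph offers Fisher's exact test, but only for comparing baseline characteristics.

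The binary outcomes in Section 5 differ widely in likely frequency. One efficacy endpoint is "Number of patients with stimulation failure: defined as no follicular growth after 1 week of adequate controlled ovarian stimulation administration", with no expected rate. Another begins "Number of patients with poor response: defined as retrieval of" and takes four oocytes or fewer as the cut-off. Complications of the oocyte/embryo cryopreservation procedures are listed as a safety endpoint.

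Section 5 compares the two stimulated cohorts with each other for efficacy. For safety it compares each of them separately with the non-stimulated cohort, whose members decline oocyte/embryo cryopreservation.

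**The concern.** A logistic model fitted by maximum likelihood has no finite odds ratio when one of the compared groups has no events. The iterations drift towards infinity, the reported standard error becomes huge, and a Wald p-value moves towards 1 whatever the data show. With a handful of events in total, the estimate may be finite, but a model with several covariates is unstable. Adjustment matters here, because the stimulated cohorts are defined by country and are not randomised.

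Stimulation failure is a natural candidate for sparse data. It means no follicular growth at all, in women who must meet an ovarian-reserve criterion ("only applicable for patients who undergo controlled ovarian stimulation for embryo/oocyte cryopreservation"). At stake is whether named secondary outcomes get an interpretable comparison, and whether the substitute method is fixed before the tables are seen.

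**Working it through.** **Inputs.** From Section 5: 113 patients in each stimulated cohort ("With 113 patients in the standard-stimulated cohort and 113 in the letrozole-stimulated cohort, assuming a mean number of mature oocytes collected of 6.1"), and for the non-stimulated cohort "it is estimated to enroll 339 patients in the non-stimulated cohort". The documents give no rate for stimulation failure or procedure complications, so the rates below are assumptions shown as a range.

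**1. The plan's own figure.** Section 5 sizes the study to "reject the null hypothesis of equal means when the population mean difference is 1.5 mature oocytes collected", with SD 4.0 and two-sided alpha 0.05. The noncentral t distribution gives n = 112.6, so 113 per cohort, with power 0.801. The stated figure reproduces. It concerns a count, and this point does not touch it.

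**2. What happens with a zero cell: 0/113 versus 6/113.**
- Maximum-likelihood logistic regression: log odds ratio 21.7, SE 12,324, Wald p = 0.999. The first two values depend only on where the software stops iterating; the true maximum is at infinity.
- Fisher: 2 × C(113,6)/C(226,6) = 0.029.
- Likelihood-ratio test on the same model: chi-square 8.48, p = 0.004. The odds ratio is still infinite.
- Firth estimate (0.5 added to each cell): (6.5 × 113.5)/(107.5 × 0.5) = 13.7. Its approximate Wald interval is 0.76 to 247, which includes 1.
- Penalised-likelihood test, from the same half-added counts. Full model: 0.5 ln(0.5/114) + 113.5 ln(113.5/114) + 6.5 ln(6.5/114) + 107.5 ln(107.5/114) = −28.14. Null model: 7 ln(7/228) + 221 ln(221/228) = −31.28. Twice the difference is 6.26, p = 0.012.

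The choice of test therefore matters as much as the choice of estimator.

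**3. How often a stimulated cohort has no events.** With a common rate p, P(at least one empty cohort) = 1 − [1 − (1 − p)^113]². Expected total events are 226p.

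| Assumed common rate | Expected total events | P(at least one empty cohort) |
|---|---|---|
| 0.5% | 1.1 | 81% |
| 1% | 2.3 | 54% |
| 2% | 4.5 | 19% |
| 3% | 6.8 | 6% |
| 5% | 11.3 | 0.6% |

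Even at 3%, where an empty cohort is unlikely, about 7 events are too few for a model with more than a very few covariates.

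**4. How often a Wald test would hide a difference that Fisher detects because of an empty cohort.** With an empty cohort of 113, Fisher first falls below 0.05 at 0 versus 6 (0 versus 5 gives 0.060). The chance of 0 versus at least 6 is as follows:
- Equal rates of 0.5%, 1% and 2%: 0.003%, 0.07% and 0.5%. No true difference exists to be missed here.
- 1% versus 2%: 0.9%.
- 1% versus 5%: 0.321 × 0.499 = 16%.
- 1% versus 7%: 0.321 × 0.810 = 26%.

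**5. Procedure complications.** Patients who do not undergo oocyte/embryo cryopreservation cannot have its complications, so the comparator is 0/339 by construction. Against 3/113, the Wald p is 0.999 and Fisher gives (113 × 112 × 111)/(452 × 451 × 450) = 0.015. No assumption about the chance of an empty cohort is needed.

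**6. A common outcome for contrast.** Taking the planning means 6.1 and 7.6 with SD 4.0 as a rough stand-in for oocytes retrieved, a normal approximation gives Φ((4.5 − 6.1)/4) = 34% and Φ((4.5 − 7.6)/4) = 22% with four or fewer. A negative binomial gives 40% and 23%. These means are for mature oocytes, so total retrieval would give somewhat lower shares. At such rates logistic regression works normally.

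**The case against.** The strongest reply is that the sentence is merely unspecific. It names neither maximum likelihood nor the Wald test. A likelihood-ratio test of the same model gives p = 0.004 for 0 versus 6, and Firth regression is itself logistic regression. A standard error above 12,000 is also hard to overlook, and the raw counts are themselves the listed endpoints. This stands in part: a p-value near 1 is not a necessary result of the plan. But the likelihood-ratio test leaves the odds ratio infinite, and its type I error is inflated at these rates (6.8% at 1% versus 1%, 9.4% at 2% versus 2%). Unqualified logistic regression is ordinarily read as maximum likelihood.

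Three stronger readings are tempting, and the documents do not support them:
- **That rarity alone makes the estimate infinite.** An empty cohort or separation by covariates is required: 1/113 versus 8/113 gives a finite estimate with Wald p = 0.045. Nor is rarity established. No rate is given, and the reserve criterion joins its parts by and/or, so one part can suffice.
- **That 81%, 54% and 19% are chances of missing a real difference.** They assume equal rates, so there is no difference to miss.
- **That malformations will fail in the same way.** The background reports that "A total of 25 children were born from 18 pregnancies without fetal anomalies or malformations", but that is a single letrozole series. Section 5 lists malformations apart from the efficacy and safety endpoints that it sends to a cohort comparison, in terms that read as descriptive.

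**Conclusion.** The point holds as a minor, secondary-endpoint improvement. The only method named for binary outcomes yields no finite odds ratio when a cohort is empty and an unreliable adjusted one when events are few, and the plan provides no alternative.

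For stimulation failure the size depends on an unknown rate: an empty cohort is likely at or below 1%, plausible at 2% and uncommon from 3% upward. Concealment of a real difference needs both a Wald test and widely separated rates, as in the 16% at 1% versus 5%. For procedure complications the zero follows from a literal reading of Section 5, with no assumed rate. The sample size, the primary endpoint and poor response are unaffected.

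**What to change.** Amend the sentence in Section 5 and the synopsis along these lines:
- For a dichotomous outcome with a zero or sparse cell, the unadjusted comparison uses Fisher's exact test with an exact confidence interval for the difference in proportions.
- Any adjusted odds ratio comes from Firth-penalised logistic regression, with a penalised-likelihood test and interval and very few covariates.
- Logistic regression as now stated is kept for commoner outcomes such as poor response.

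The sponsor should define sparse in advance as a stated number of events. Add that complications of oocyte/embryo cryopreservation are reported within, or compared between, the two stimulated cohorts, not tested against the non-stimulated cohort.

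The cost is a few lines of text and no new data. The downside is that Fisher's test is slightly conservative and unadjusted. In cohorts defined by country it cannot separate protocol from centre or case mix, and it should be reported with that caveat.

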## 6. QUALITY CONTROL AND QUALITY ASSURANCE

### 6.1. Quality control

Throughout the study the dedicated sponsor study team members verify the data to ensure that:

- the rights and well-being of subjects are protected
- the reported trial data are accurate, complete and verifiable from source documents
- the conduct of the trial is compliant with the International Conference on Harmonisation (ICH) – Good Clinical Practice (GCP), the applicable regulatory requirements, the study protocol and the study guidelines.

Quality control activities combine central monitoring and clinical site monitoring. Monitoring activities may be performed remotely and/or on site according to the study needs.

### 6.2. Quality assurance

To ensure compliance with the protocol, study documentation, GCP and all applicable regulatory requirements, the sponsor may conduct a quality assurance audit on participating site. Regulatory agencies may also conduct a regulatory inspection of the study. The principal investigators must inform the sponsor in case an inspection from Regulatory agencies has been scheduled at their sites.

Such audits/inspections can occur at any time during or after completion of the study. If an audit or inspection occurs, the investigator and institution must agree to allow the auditor/inspector direct access to all relevant documents and to allocate his/her time and the time of his/her staff to the auditor/inspector to discuss findings and any relevant issues in the presence of the sponsor, as needed or required.

## 7. REGULATORY AND ETHICAL CONSIDERATIONS

### 7.1. Regulatory considerations

The study is submitted by the principal investigators or the national coordinator or the sponsor (or its legal representative), in accordance with local regulations, to and approved by an appropriate Independent Ethical Review Committee (IEC) / Institutional Review Board (IRB) and a Regulatory Authority if required by the national laws of the countries where the study is conducted. Local regulatory approval may also be required.

The study cannot start in a participating site before written approval by corresponding Ethics Committee(s) has been obtained and the local regulatory requirements have been complied with.

The sponsor provides a copy of the final protocol, subject information sheets, consent forms and all other relevant study documentation for local required submissions.

The principal investigators and the sponsor ensure that the study is conducted in full conformance with the principles of the “Declaration of Helsinki” 1964, as revised from time to time and with the laws and regulations of the country in which the research is conducted, whichever affords the greater protection to the individual. The study must fully adhere to the principles outlined in “Guideline for Good Clinical Practice” ICH-E6 Tripartite Guideline (January 1997) and with national laws.

For the Study conducted in the EU/EEA countries, the principal investigators ensure compliance with the ICH GCP and with the EU Data Protection Directive (95/46/EC).

## 7.2. Informed consent form

It is the responsibility of the principal investigators or a person designated by the principal investigators (if acceptable by local regulations) to obtain a signed written informed consent from each potential subject prior any study related procedure being carried out. The informed consent is applicable throughout the subject's participation to the study.

The Informed Consent form (ICF), approved by an appropriate IEC / IRB, is provided by the sponsor to the principal investigators as a separate document dated and version controlled to this protocol.

The ICF describes in details the aims, the procedures, the methods, the interventions, the anticipated benefits, the possible adverse events and the potential hazards of the study. Many events are likely to occur which meet the definition of serious adverse events and which are due explicitly to the patients' underlying malignancy management or chemotherapy treatment. For this study, these adverse events or SAE will be exempt from report or declaration in the CRF, except if unexpected or suspected to be linked to the ovarian stimulation.

The principal investigators or designee also explain to the subject that the participation to the study is voluntary and that the subject is free to refuse to enter the study or to withdraw from it at any time, for any reason without any impact in the subject's subsequent care.

All subjects receive the appropriate version of the written information and are asked to read and review it.

For subjects not qualified to give or incapable of giving consent, written consent must be obtained from the legal representative. In the case where both the subject and his or her legal representative are unable to read, an impartial witness should be present during the entire informed consent discussion. After the subject and/or legal representative has/have orally consented to participation in

the trial, the witness's signature on the form will attest that the information in the consent form was accurately explained and understood.

The written ICF must be dated and personally signed by the principal investigators or authorised sub-investigator and the subject taking consent (or subject legal representative).

The original copy of the signed ICF will be retained in investigator's study file (ISF) and must be made available for monitoring, audit or inspection. A copy of the signed ICF is given to the subject.

In case of new information that might affect the subject's willingness to continue participating in the study or results in significant changes in the risk/benefit assessment, the ICF should be reviewed and updated if necessary. All subjects, including those already being treated, should be informed of the new information, given a copy of the revised form, and give their consent to continue in the study.

### **7.3. Subject identification**

The principal investigators or any authorised study member staff must assure that subjects' identity is maintained confidential and that their identities are protected from unauthorised parties. Personal medical information is always treated as confidential.

On CRFs or any other study document, subjects shall not be identified by their names or initials or social security number or patient chart number, but always by the assigned subject study identification code and their date of birth (either complete or partial as allowed by national laws) in order to avoid identification errors.

The principal investigators should create and maintain up-to-date in the ISF the Subject screening/enrolment/identification log. This ICH-GCP log is required for documenting chronically

any screened subject, their name, their assigned study number in case of study enrolment or the reason in case of non-enrolment. A note is made in the hospital medical records that the subject is participating in the study.

The name of a subject is neither asked for nor recorded by the sponsor. If subjects' names or any other confidential subject information are included by error on copies of documents submitted to the sponsor, they are obliterated and the assigned subject study identification code added to the document by the sponsor. Moreover, the sponsor asks to the principal investigators or any authorised study member staff to also obliterate this information on the documents that he/she has submitted.

Documents (e.g. subjects' written ICFs) not for submission to sponsor should be maintained by the principal investigators in strict confidence.

